### Materials and Methods

- This study will be a phase 2, randomized, prospective, double-blind, investigator-initiated, parallel-group, placebo-controlled clinical trial conducted at the Hospital Civil de Guadalajara “Fray Antonio Alcalde”, Guadalajara, Mexico. All patients with AKI receiving nephrology consultation will be considered for inclusion.
- The diagnosis of AKI will follow the Kidney Disease: Improving Global Outcomes (KDIGO) serum creatinine criteria. In accordance with the recommendations of the 31st Acute Disease Quality Initiative Group regarding the design of clinical trials for AKI treatments, the subphenotype of patients at the highest risk of post-AKI infections will be selected. This study will be considered a phase 2 randomized, double-blind, placebo-controlled trial meeting efficacy (AKI trajectory and eGFR evaluation), feasibility (patient recruitment and protocol adherence), and safety (adverse events and drug reactions) objectives.
- Group randomization will be performed using the clinical trial randomization tool available at <http://www.winepi.net/f108.php>, employing traditional block randomization. Sequences for each arm and stratum will be generated using maximal asymptotic randomization.
- Patients will be recruited on an outpatient basis to document any infectious event of any kind occurring within the first 90 days, as well as cases of rehospitalization due to infection within the same period at the Hospital Civil de Guadalajara “Fray Antonio Alcalde”.

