#### Sampling Method

Potential participants for this study will be identified during routine hospital rounds for patients with acute kidney injury (AKI) and through concurrent review of medical records to confirm eligibility. If a patient is deemed eligible, the principal investigator will contact them to explain the study and provide a participant information and consent form.

After discussion with the patient and family members, the nephrology staff will obtain written informed consent prior to any study-related evaluations.

The intervention drug will be trimethoprim–sulfamethoxazole 800/160 mg, administered under double-blind conditions. Blinding will be achieved by ensuring that participants do not witness preparation of the study medication, and by assigning unblinded study personnel—who will not participate in outcome assessments—to handle preparation and administration.

The placebo will consist of magnesium tablets, administered at the same frequency—one tablet every 48 hours for three months.

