## Operationalization of Variables

### Independent Variable:

- Treatment: Administration of the study drug versus placebo (categorical variable with two levels: active treatment or placebo).

Dependent Variables (Primary Outcomes):

- Development of gastrointestinal infections — categorical nominal binary variable (yes/no)
- Development of upper respiratory infections — categorical nominal binary variable (yes/no)
- Development of lower respiratory infections — categorical nominal binary variable (yes/no)
- Development of urinary tract infections — categorical nominal binary variable (yes/no)
- Development of soft tissue infections — categorical nominal binary variable (yes/no)
- Rehospitalization due to infection — categorical nominal binary variable (yes/no)
- Development of septic shock — categorical nominal binary variable (yes/no)
- Requirement for long-term renal replacement therapy — categorical nominal binary variable (yes/no)
- Death from any cause — categorical nominal binary variable (yes/no)
- Progression to chronic kidney disease or  $\geq 50\%$  decline in eGFR — categorical nominal binary variable (yes/no)
- Worsening renal function with  $\geq 25\%$  decline in eGFR due to infection — categorical nominal binary variable (yes/no)
- Presence of hyperkalemia — categorical nominal binary variable (yes/no)
- Adverse drug reactions — categorical nominal variable

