## Data Collection and Observation Techniques

Data will be collected through automated extraction from the institutional electronic medical record system. Additional potential contributors to AKI—such as nephrotoxic medications (aminoglycosides, nonsteroidal anti-inflammatory drugs, and vancomycin)—will also be considered.

The presence of anaphylactic shock will be documented, and relevant biochemical parameters, such as serum iron levels and transferrin saturation, will be recorded for analysis.

Indications for renal replacement therapy (RRT) will include:

- Fluid overload refractory to diuretics
- Severe hyperkalemia
- Severe metabolic acidosis
- Uremic manifestations such as encephalopathy, pericarditis, or seizures

The study will be submitted to the Institutional Review Board (IRB) of the Hospital Civil de Guadalajara “Fray Antonio Alcalde” and registered at ClinicalTrials.gov with the corresponding registration number.

This research will adhere to the ethical principles outlined in the Declaration of Helsinki and will be designed in accordance with CONSORT (Consolidated Standards of Reporting Trials) guidelines.

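### Adherence is part of the feasibility objective and the elimination criteria depend on it, but the protocol names no variable, table or data source that captures tablet intake, stop date or reason for stopping

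*Protocol*

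**What the plan says.** - **Objective.** Protocol, Materials and Methods, gives the trial three kinds of objective: efficacy, "feasibility (patient recruitment and protocol adherence), and safety (adverse events and drug reactions) objectives". Adherence is thus one of two named components of feasibility.
- **Setting and regimen.** The same section says "Patients will be recruited on an outpatient basis to document any infectious event of any kind occurring within the first 90 days". Sampling Method has the placebo "administered at the same frequency—one tablet every 48 hours for three months", and the Research Question sets the active tablet at the same interval for 90 days.
- **Variables.** Under Operationalization of Variables, treatment appears only as "Treatment: Administration of the study drug versus placebo (categorical variable with two levels: active treatment or placebo". Thirteen dependent variables follow, ending with "Adverse drug reactions — categorical nominal variable". None concerns intake, stopping or reason for stopping.
- **Data source.** Data Collection and Observation Techniques states: "Data will be collected through automated extraction from the institutional electronic medical record system". It adds some clinical and laboratory items, none on study tablets.
- **Reporting.** Presentation of Information plans a demographic table, an infection table and a Kaplan–Meier curve. Secondary Objectives has no adherence item either.
- **Rules that use intake.** Elimination Criteria remove patients who stopped the antibiotic in part or altogether before three months, or whose dose departed from the prescription. Statistical Analysis adopts intention to treat among randomized participants who receive the intervention.

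**The concern.** The protocol declares an objective and writes rules that both need exposure data, and then describes no way of obtaining those data. A routine hospital record would not be expected to show whether a patient at home took a blinded tablet every second day, and the protocol does not say that anyone will enter this in the record.

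Three things are at stake:

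- The adherence component of feasibility would have no data behind it.
- The elimination categories would depend on which lapses reached the notes. That is likely to favour patients with more clinic contact or more symptoms, who may differ between arms.
- If infection rates turned out similar, the trial could not say whether the drug failed or was not taken. Adverse events could not be related to exposure.

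This cannot be left to a statistical analysis plan, which can only analyse what was recorded. Tablet counts and stop dates cannot be reliably rebuilt after follow-up ends.

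**Working it through.** **Step 1. Match each need to its data.**

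| Where intake is needed | What is needed | What the protocol provides |
|---|---|---|
| Feasibility objective (Materials and Methods) | Adherence per patient | No variable, no planned table |
| Elimination for stopping early | Date of last tablet, or missed tablets | No variable, no stated source |
| Elimination for a different dose | Dose actually taken | No variable, no stated source |
| Analysis set (Statistical Analysis) | Whether the intervention was received | Assigned arm only |

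No tablet count, return log, diary, interview or drug level is described anywhere. The scheduled exposure is 90 days / 2 days per tablet = 45 tablets per patient.

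**Step 2. Reproduce the sample size.** Inputs from Sample Size and Statistical Analysis: p1 = 0.59, p2 = 0.295, two-sided 5%, power 90%, 60 per group. The mean proportion is p̄ = (0.59 + 0.295)/2 = 0.4425.

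n = [1.96·√(2p̄(1−p̄)) + 1.2816·√(p1(1−p1) + p2(1−p2))]² / (p1−p2)²

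= [1.96·0.7024 + 1.2816·0.6707]² / 0.0870 = 57.5, so 58 per group.

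With the pooled variance in both terms the result is 59.6, so 60, which is the protocol's figure. Power at n = 60:

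Φ{[0.295·√60 − 1.96·0.7024] / 0.6707} = Φ(1.354) = 91.2%.

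The stated 60 per group is reproduced. The full 59% to 29.5% contrast goes into it, so it contains no allowance for tablets not taken.

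**Step 3. Context: what non-adherence could do.** The documents give no adherence rate, so a range is assumed. Let a fraction f of active patients stop at once and carry the control risk. The active-arm rate is then 0.295(1−f) + 0.59f.

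| f (assumed) | Active rate | Power at 60 per group |
|---|---|---|
| 0 | 29.5% | 91% |
| 10% | 32.5% | 84% |
| 20% | 35.4% | 74% |
| 30% | 38.4% | 62% |
| 40% | 41.3% | 49% |

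Example, f = 20%: the difference is 0.59 − 0.354 = 0.236 and p̄ = 0.472. Power = Φ{[0.236·√60 − 1.96·0.7060] / 0.6860} = Φ(0.648) = 74%.

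The model keeps stoppers in the analysis, as intention to treat requires. It does not describe what happens if the Elimination Criteria remove them.

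**Step 4. What the table does and does not show.** It shows that ordinary non-adherence could by itself produce a null result. It does not measure the loss from failing to record adherence, because counting tablets would not raise any of these powers. It would show where in the range the trial lies.

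**The case against.** The strongest reply is that the protocol leaves a procedure unstated rather than ruling it out. Much of this stands.

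- A reader might infer that the hospital record is the only data source. The text does not say so. Patients have nephrology follow-up (Study Population), are monitored for 90 days (Observation Unit), and study medication is handled by assigned staff. Any of these contacts could supply intake data. But no section says they will, and the role of the medication handlers is described as a blinding measure: "assigning unblinded study personnel—who will not participate in outcome assessments—to handle preparation and administration".
- A reader might infer that whatever is absent from the variable list goes uncollected. The list is not exhaustive: it omits new AKI episodes and all-cause rehospitalization, which are secondary objectives, and the data collection section adds items of its own. Here, however, the item is absent from the variables, the planned tables and the stated source alike.
- A reader might infer that a whole declared aim fails. Recruitment, the other half of feasibility, is unaffected. Protocol adherence is also undefined and may include visit completion or retention.
- A reader might infer that a null result could not be interpreted. An intention-to-treat comparison still estimates the effect of assignment. What is lost is the ability to explain a null.

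The Elimination Criteria show that the authors expect to know who stopped. That softens the charge of oversight, but it also makes the missing method matter more.

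**Conclusion.** The point holds in limited form. Adherence is a named component of the feasibility objective, and the elimination rules turn on stopping and dose, but the protocol contains no intake, stop-date or discontinuation item and names no source suited to supplying one. Followed as written, the adherence component has no planned data, elimination is applied only where stopping happens to be noted, and a null result cannot be divided between an ineffective drug and tablets not taken.

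The documents do not support saying that feasibility as a whole fails, that the record is the sole source, or that a null would be meaningless. The fall in power from about 91% to between 84% and 49% is context. It rests on assumed stopping fractions of 10% to 40%, immediate stopping, full reversion to 59%, and the protocol's own 59% versus 29.5%. That the hospital record would not show home intake is a reasonable expectation, not something the protocol states.

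**What to change.** 1. Add to Operationalization of Variables, identically for both arms: date of first tablet, date of last tablet, reason for stopping, and tablets returned out of those dispensed (about 45 scheduled).
2. In Data Collection and Observation Techniques, name the source as a dispensing and return log completed at nephrology follow-up contacts, and state when those contacts and any resupply occur, since no schedule is given.
3. Protect the blind. Either staff blinded to arm record everything, or the medication handlers only count tablets while blinded staff take the reasons for stopping. Those reasons will often be adverse reactions, a listed outcome, and Sampling Method bars the unblinded staff from outcome assessment. The protocol does not say whether the two tablets look alike. If they do not, the second arrangement is needed, with wording that a tablet count is not an outcome assessment.
4. Define protocol adherence, and report the proportion of scheduled tablets taken and the discontinuation rate by arm as the feasibility outcome. Add this to Presentation of Information.
5. Reconcile the Elimination Criteria with the intention-to-treat set in Statistical Analysis, so that recorded stopping describes exposure and does not by itself decide who is analysed.

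Cost: protocol wording, a short log as a small new procedure, and a few minutes per visit. Tablet returns will be incomplete and can overstate intake, so the measure will be imperfect. The change should be made early, because intake that goes unrecorded cannot be recovered.

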#### Statistical Analysis

An intention-to-treat approach will be adopted, including all randomized participants who receive the intervention, for both primary and secondary outcomes.

Categorical variables will be expressed as counts and percentages (%) and compared using either the chi-square test or Fisher’s exact test, as appropriate.

Continuous variables will be reported as median values (IQR), since normal distribution is not expected according to the Shapiro–Wilk test; between-group comparisons will be performed using the Mann–Whitney U test.

A repeated-measures analysis of variance (ANOVA) will be used to compare variables over time between groups. A Kaplan–Meier survival curve will be plotted for both groups and compared using the log-rank test. Missing data will be imputed using the mean linear interpolation method.

All statistical tests will be two-tailed, and a p-value < 0.05 will be considered statistically significant.

The analyses and figures will be performed using MedCalc software (Version 22.0.21, Ostend, Belgium) and GraphPad Prism (Version 10.2.3, Boston, Massachusetts, USA).

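### Allocation is described by stratum, with no factor defined and two sequence methods named, while every planned test is unstratified; if the strata predict infection the tests are mildly conservative (minor)

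*Protocol*

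**What the plan says.** **Allocation (Protocol, Materials and Methods).** One bullet describes the randomisation. Its first sentence names an online tool, "employing traditional block randomization". Its second reads "Sequences for each arm and stratum will be generated using maximal asymptotic randomization". The protocol gives no stratification factor and no number of strata, there or elsewhere.

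**Analysis (Protocol, Statistical Analysis).** Tests are assigned by type of variable:

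- Binary outcomes: "Categorical variables will be expressed as counts and percentages (%) and compared using either the chi-square test", with Fisher's exact test as the alternative.
- Continuous outcomes: "between-group comparisons will be performed using the Mann–Whitney U test".
- Repeated measures: "A repeated-measures analysis of variance (ANOVA) will be used to compare variables over time between groups".
- Time to event: "A Kaplan–Meier survival curve will be plotted for both groups and compared using the log-rank test".

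None of these carries a stratum or a covariate. Tests are two-sided at 5%.

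**Sample size (Protocol, Sample Size).** 60 per group for 59% v 29.5% with 90% power. Strata are not mentioned.

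**The concern.** There are two linked problems.

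First, the allocation cannot be carried out as written. Two methods are named for the same sequences. A sequence is the thing that assigns arms, so it is generated once per stratum and not once per arm. And with no factor defined, nobody can say which stratum a patient belongs to.

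Second, if the allocation is stratified, the analysis does not match it. Balance within strata removes the between-stratum variation from the treatment contrast. An unstratified test still counts that variation in its variance. If the strata predict infection, the standard error is too large, the p-value too high and the confidence interval too wide. At stake is some efficiency in a trial of 120 patients.

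**Working it through.** **1. The plan's own figure.** Inputs from Sample Size: p1 = 0.59, p2 = 0.295, two-sided 5%, 90% power. With mean 0.4425 and difference 0.295:

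n = 2 × 0.4425 × 0.5575 × (1.960 + 1.282)² / 0.295² = 59.6, so 60 per group.

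The stated size is reproduced. A normal approximation gives power of 91.2% at 60 per group.

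**2. Assumptions.** The protocol gives no stratum risks, so these are assumed: two strata of 60 patients, 30 per arm in each, and mean control risk 59%. Three spreads are used (50/68%, 40/78%, 30/88%), plus 59/59% for strata that predict nothing.

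**3. Type I error by formula.** The unstratified test uses the total variance V_T = 0.59 × 0.41 = 0.2419. The contrast actually varies with the within-stratum variance V_W, the mean of p(1 − p) over strata. The true level of a nominal 5% test is about 2[1 − Φ(1.96 √(V_T/V_W))].

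| Control risks | V_W | V_T/V_W | True level |
|---|---|---|---|
| 59/59% | 0.2419 | 1.000 | 5.0% |
| 50/68% | (0.2500 + 0.2176)/2 = 0.2338 | 1.035 | 4.6% |
| 40/78% | (0.2400 + 0.1716)/2 = 0.2058 | 1.175 | 3.4% |
| 30/88% | (0.2100 + 0.1056)/2 = 0.1578 | 1.533 | 1.5% |

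**4. Simulation.** At least 200,000 trials per scenario compared the Pearson chi-square test with the Cochran-Mantel-Haenszel test (CMH, no continuity correction). The CMH statistic is Z = Σ(x_h − T_h/2) / √Σ{m² T_h(2m − T_h) / [(2m)²(2m − 1)]}, where m = 30, x_h is the number of treated events and T_h all events in stratum h. For power, the common within-stratum odds ratio was set so that the overall treated risk equals the planned 29.5%.

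| Control risks | Odds ratio within strata | Type I error, unstratified v CMH | Power, unstratified v CMH | Loss (points) |
|---|---|---|---|---|
| 59/59% | 0.291 | 5.1% v 5.1% | 91.6% v 91.6% | 0 |
| 50/68% | 0.279 | 4.8% v 4.9% | 92.0% v 92.1% | 0.1 |
| 40/78% | 0.235 | 3.5% v 5.1% | 93.2% v 94.6% | about 1.5 |
| 30/88% | 0.153 | 1.6% v 5.1% | 95.2% v 98.2% | 3 |

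Repeat runs differ by about 0.1 to 0.2 points. In every row the unstratified test keeps more than 90% power.

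**5. How strong are real strata likely to be?** The largest hazard ratio for infection that the Background section quotes is 1.55, for transition from AKI to CKD. Taking two equal groups with mean risk 59% and solving 1 − (S + S^1.55)/2 = 0.59 gives risks of about 51% and 67%, close to the 50/68% row. That cohort differs in population and follow-up, so this is only a guide. By comparison, 30/88% is an odds ratio of about 17 between strata: (0.88/0.12) / (0.30/0.70) = 17.1.

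**6. Lower event rate.** Sample Size also mentions an infection rate of about 30%. At 30% v 15% (the halving is an assumption), the loss is about 1 point for strata at 20/40%, 5.6 points at 10/50% and 9.5 points at 5/55%. Unstratified power there is only about 51% to 52% whatever the strata. That low power comes from the event rate and is a separate matter.

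**The case against.** **The section may only be a summary.** It describes tests by type of variable and does not rule out stratification, and a SAP that is not shown might add it. This has some force for the analysis half. It has none for the allocation half: two methods and an undefined stratum sit in the protocol itself and must be settled before the first patient is randomised.

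**Allocation may not be stratified at all.** The only mention of a stratum is in the sentence that is itself unclear. If no strata are used, the mismatch with the analysis disappears and only the wording remains. This stands, and the fix allows for it.

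**A reader might infer a serious loss of power.** If an odds ratio of 0.25 is assumed within strata of 30/88%, power is about 72% unstratified against about 85% for CMH. With 0.29 within strata of 40/78%, it is about 84% against 86%. But those settings give overall treated risks of 37.2% and 33.4%, a smaller effect than the planned 29.5%. Their low power comes mainly from that smaller effect. At the planned effect the losses are 3 and about 1.5 points.

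**A reader might also infer too many false positives, or that the planned 90% power fails.** Neither is supported. The error lies in the conservative direction, and unstratified power stays above 90% in every scenario at the planned rates.

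**Conclusion.** The point holds, conditionally, and is minor. What is certain from the text is that the allocation description names two methods, implies a sequence per arm and refers to strata that are never defined, and that every listed test is unstratified. The statistical consequence follows only if strata are used and predict infection. Its size cannot be derived from the protocol, because it depends on stratum risks that are assumed here. Over the range examined at the planned rates it runs from nothing to a 3-point loss of power, with a true type I error between about 5% and 1.6%. For strata about as strong as the predictors quoted in the Background, the loss is about 0.1 point.

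**What to change.** **Materials and Methods.** Keep one sequence method and delete the other. State that one sequence is generated per stratum, and name a small number of stratification factors. If allocation is not to be stratified, delete the reference to strata. The factors have to be named: without them neither the allocation nor a stratified test can be run.

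**Statistical Analysis, only if strata are kept.** Analyse binary infection outcomes with the Cochran-Mantel-Haenszel test, reporting a Mantel-Haenszel risk difference or risk ratio with its 95% confidence interval. Analyse time to infection with a log-rank test. Stratify both by the randomisation factors.

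**Cost.** A few sentences of wording and no extra outcome data. When the strata turned out not to be prognostic, CMH lost no power at the planned rates. The one constraint is that the number of strata must stay small for 120 patients.

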### Theoretical and Conceptual Framework

Infections are among the least studied consequences of AKI. Although kidney diseases are well-recognized risk factors for infections—and infections remain one of the leading causes of death among patients with renal disease—the underlying mechanisms of this secondary immunodeficiency remain poorly defined [Steiger S]. Regarding the bidirectional relationship between AKI and infections, the recently published NARA-AKI prospective study demonstrated that postoperative AKI in non-cardiac surgery was associated with increased hospitalizations due to infections [Tagawa M, Kellum JA]. Beyond AKI, patients with chronic kidney disease (CKD) are more vulnerable to infections and exhibit worse outcomes than cohorts without CKD [Xu H, Su G]. Interestingly, not only the progression from AKI to CKD but also the decline in eGFR—*independent* of baseline or post-AKI eGFR—was independently associated with infection risk.

Several mechanisms may explain this increased susceptibility to infection. The immune dysfunction of CKD—characterized by impaired innate and adaptive immunity, decreased clearance of proinflammatory cytokines, and even epigenetic modifications in hematopoietic stem cells—adds to the alterations seen in AKI, such as disrupted kidney-immune system crosstalk, changes in immune cell composition and function, and an exaggerated inflammatory response [LaFavers K, Syed-Ahmed M]. Nevertheless, the precise pathophysiology of the elevated infection risk in patients transitioning from AKI to CKD remains incompletely understood.

Finally, a retrospective cohort study (Griffin BR) showed that recovery from AKI was associated with a 4.5-fold increase in the likelihood of infection (OR 4.53 [95% CI, 2.43–8.45];  $p < 0.0001$ ) within 30 days after hospital discharge. Moreover, the association between AKI and subsequent infection remained significant at 31–60 days and 91–365 days post-discharge, but not during the 61–90-day interval.

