### Study Objectives

#### Primary Objective:

To reduce the risk of infections within 90 days following hospital discharge after a severe episode of acute kidney injury (AKI).

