### Study Population

Patients diagnosed with severe acute kidney injury (AKI) who have been discharged from the hospital and receive nephrology follow-up at the Hospital Civil de Guadalajara “Fray Antonio Alcalde”, Guadalajara, Mexico. This group will include patients with diverse demographic and clinical characteristics who meet the inclusion criteria established in the study protocol.

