### Observation Unit

Patients diagnosed with severe AKI will be monitored for a period of 90 days after hospital discharge. Each participant will be evaluated based on infection incidence, rehospitalization, adverse events, and other health outcomes related to trimethoprim–sulfamethoxazole administration. Observation will focus on collecting clinical data and health outcomes specific to each participant.

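### The 90-day infection window runs from hospital discharge, but nothing ties randomisation or first dose to discharge, so any gap dilutes the treatment effect

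*Protocol*

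**What the plan says.** Two sections of the protocol fix the clock at discharge. The Primary Objective is "To reduce the risk of infections within 90 days following hospital discharge". Under Observation Unit, patients "will be monitored for a period of 90 days after hospital discharge".

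Two sections describe enrolment after discharge. Materials and Methods states: "Patients will be recruited on an outpatient basis to document any infectious event of any kind occurring within the first 90 days". The origin of the 90 days is not given in that sentence. Study Population consists of patients "who have been discharged from the hospital and receive nephrology follow-up".

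Two sections point toward the hospital stay. Sampling Method finds candidates on ward rounds and by record review, with consent after discussion with patient and family, but does not say whether consent comes before or after discharge. Control Group Definition describes controls as identified while in hospital and sent home on usual care with no prophylaxis added.

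The Research Question, Working Hypothesis and Sampling Method set a course of 90 days or three months. None gives its first day. No section gives a day of randomisation relative to discharge or says what happens to an infection that begins before randomisation.

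**The concern.** The outcome window and the treatment course have the same length but are not given the same origin. If the first tablet comes d days after discharge, the first d days of the window are untreated in both arms, and the last d days of the course fall outside it. With d = 14, only 90 − 14 = 76 treated days lie inside the window.

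Infections in the untreated days occur equally in both arms on average, so they add events without adding any difference. The infection outcomes under Operationalization of Variables are yes/no, so a patient infected before the first tablet would already be a yes, whatever the treatment does later. Data Collection relies on automated extraction from the hospital record, which could capture such events.

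The same ambiguity affects the Kaplan–Meier curve and log-rank test, which need a time origin. At stake is power in a trial of 2 × 60 = 120 patients, and an estimate that understates whatever effect the drug has.

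**Working it through.** **Inputs.** From Sample Size: 59% versus 29.5%, 60 per group, 90% power. From Statistical Analysis: two-sided 0.05. Assumed, because the protocol gives none: the gap d between discharge and first dose, a constant hazard over the 90 days, a treatment effect that begins at the first dose, and counting of events before that dose.

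**The plan's own figure.** The simple pooled formula with p̄ = (0.59 + 0.295)/2 = 0.4425 gives

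n = 2(1.96 + 1.2816)² × 0.4425 × 0.5575 / 0.295² = 59.6, so 60 per group.

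The stated size is reproduced. A formula with pooled variance under the null and separate variances under the alternative gives 58. Power at 60 per group is

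Φ{[Δ√n − 1.96√(2p̄(1 − p̄))] / √(p₁(1 − p₁) + p₂(1 − p₂))} = Φ{(2.285 − 1.377)/0.671} = Φ(1.354) = 91%.

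**Adding a gap.** Cumulative 90-day hazards are −ln(1 − 0.59) = 0.892 for control and −ln(1 − 0.295) = 0.350 for active, a hazard ratio of 0.392. The control risk stays at 59%. The active-arm risk in a window starting at discharge is

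1 − exp{−[0.892 × d/90 + 0.350 × (90 − d)/90]}.

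For d = 14 this is 1 − exp{−(0.139 + 0.295)} = 35.2%. The risk ratio is 35.2/59 = 0.60. Control risk before the first dose is 1 − exp(−0.139) = 13.0%, which is 13.0/59 = 22% of control events.

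| Assumed gap (days) | Active-arm risk | Difference (points) | Risk ratio | Power, 60 per arm | n per arm for 90% power |
|---|---|---|---|---|---|
| 0 | 29.5% | 29.5 | 0.50 | 91% | 58 |
| 7 | 32.4% | 26.6 | 0.55 | 84% | 72 |
| 14 | 35.2% | 23.8 | 0.60 | 75% | 91 |
| 21 | 37.9% | 21.1 | 0.64 | 64% | 116 |
| 30 | 41.2% | 17.9 | 0.70 | 50% | 163 |

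**Without a constant hazard.** What matters is the share of the control arm's cumulative 90-day hazard that falls before the first dose. Shares of 10%, 20% and 30% give power of 82%, 69% and 55%.

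**A lower event rate.** Sample Size also mentions an infection rate of about 30%. If that is taken as the control risk and halved to 15% (an assumption), power at 60 per arm is 50% with no gap and 36% with a 14-day gap. The conflict between the two rates is a separate matter; dilution occurs under either.

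**The case against.** The strongest reply is that there may be no gap worth the name. Sampling Method places identification on the ward, and Control Group Definition describes controls as going home without prophylaxis added, which suggests that the arms differ in what is given at discharge. On that reading the first tablet comes at or near discharge, the two clocks nearly coincide, and power stays at about 91%. The sentence in Materials and Methods could also be read as describing outpatient follow-up. This stands as a limit on size: the protocol does not show that the loss is large. It does not remove the inconsistency, because no section says that treatment starts at discharge.

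A reader might infer that the protocol counts infections before randomisation as outcomes. It does not say so. That follows only if the discharge-based window is applied as written and enrolment lags. The outcomes are worded as the development of infections, which fits new events, and detailed handling of baseline infections may sit in a statistical analysis plan that is not shown. The window itself is different: the protocol fixes it in the primary objective.

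A reader might also infer from the Theoretical and Conceptual Framework that the days lost carry the largest excess risk. That section gives an effect size (odds ratio 4.53) only "within 30 days after hospital discharge". For 31–60 and 91–365 days it reports significance without figures. It neither ranks the intervals nor shows how infections are spread over time among AKI patients.

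**Conclusion.** The point holds as a conditional one. The discharge-based window, read with outpatient recruitment and a 90-day course, is a poor choice whenever enrolment lags discharge: it admits events that treatment could not have prevented and drops the end of the course. The direction, toward no effect, is certain if such events are counted. The size is not known. It runs from no loss at a zero gap to a fall in power from 91% to 75% at 14 days and 50% at 30 days, under a constant hazard and the planned 59% versus 29.5%. The illustration also assumes that patients infected before enrolment are still enrolled; if they were not, the loss would be smaller. It should be corrected because the wording is easy to change, not because a large loss has been shown.

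**What to change.** - Reconcile Primary Objective, Materials and Methods, Study Population, Observation Unit, Sampling Method and Control Group Definition, so that they state consistently when consent, randomisation and first dose occur relative to discharge.
- Set day 0 of the infection outcome and of the Kaplan–Meier analysis at the date of randomisation in both arms. Record the first-dose date separately, since the two may differ.
- Count only infections with new onset from day 0 to day 90. Treat infections present at randomisation, or occurring between discharge and randomisation, as baseline history.
- Report the discharge-to-randomisation interval by arm as a baseline variable.

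**Cost.** The change is mainly wording and needs no extra patients. Follow-up of late enrollees runs past 90 days from discharge by the length of the gap, which may affect visit timing, and the window is no longer exactly 90 days from discharge. Inclusion Criteria sets major adverse kidney events at 90 days after AKI, so that outcome would run on a different clock and the protocol should say so. Re-anchoring removes the dilution but does not guarantee 91% power, because the 59% control risk need not apply to a window that starts later.
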